### **I. Hypotheses and Specific Aims:**

Chronic irritability is a prominent dimension of pediatric psychopathology for which evidence-based treatments are scarce, have limited efficacy, or adverse side effects. There is a need to develop novel treatments, especially those that target the neurocognitive basis of irritability. One candidate is Interpretation Bias Training (IBT), a computer-based training designed to target rapid, automatic processing of social information. In a small open trial, IBT showed promise as an acceptable, feasible treatment for irritability. However, its underlying neurocognitive targets have not been established. In order to translate IBT for clinical use, we propose to examine two promising neurocognitive targets of IBT.

**Specific Aim 1:** Establish hostile interpretation bias as a treatment target for irritability and engage it through interpretation bias training. One hundred adolescents, drawn from an outpatient psychiatric clinic with varying degrees of clinically significant irritability, will be randomized to a session of active (n=50) or sham (n=50) IBT.

Hypothesis 1.1: The degree of hostile interpretation bias is positively associated with clinical irritability

Hypothesis 1.2: Active but not sham interpretation bias training will reduce hostile interpretation bias.

**Specific Aim 2:** Establish the ability to learn benign judgments of ambiguously hostile social information as a treatment target for irritability and engage it through interpretation bias training. A subsample of 50 participants (n=25 in each active and sham group) will train during fMRI.

Hypothesis 2.1: Learning rates during active IBT will be associated with baseline irritability.

Hypotheses 2.2, 2.3: In neural systems underlying threat learning, response while learning new associations during active IBT will be related to clinical irritability in terms of both neural activity (2.2) and functional connectivity (2.3).

[figure not shown]
**Exploratory Aim 3:** Provide preliminary evidence that changes in treatment targets are related to changes in irritability. To better establish the mechanism of target engagement and gather preliminary evidence for an efficacy trial, we will measure any changes in irritability after IBT. Therefore, we hypothesize that changes in irritability following active IBT will be associated with changes in hostile interpretation bias (hypothesis 3.1) and threat system response (hypothesis 3.2).

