Hypothesis 1.2: Active but not sham, IBT will reduce hostile interpretation bias. Mixed-effects linear regression with balance point (interpretation bias) as a dependent variable and training condition (active vs. sham), and time of interpretation bias assessment (pre- or post-training) as independent variables of interest and person as a grouping variable and random effect. Similar models will test for group differences in active or sham IBT on other measures of hostile interpretation bias after training.

Hypothesis 2.1: The rate of learning new associations to ambiguous faces training will be associated with baseline irritability. For those in the active condition, linear regression will test the association between pre-training ARI (irritability) and learning rate to reversal feedback of baseline angry judgments to the two ambiguous morphs.

Hypotheses 2.2 and 2.3: Active, but not sham, IBT will evoke greater neural response in threat-learning systems. For each person, learning will be modeled with regressors coding the “value” or trialwise likelihood that a participant considers the morph to be angry. The amplitude of BOLD %signal change (activity) or amygdala covariance (generalized psychophysiological interaction; connectivity) related to these regressors represents neural response to value. Critically, these regressors represent learning itself where value is changing towards benign judgments in the active training condition to two ambiguous morphs. These will be carried forward to the second level mixed-effects linear models of the effects of morph by pre-training ARI by training condition. A voxel-wise threshold of  $p < .001$ , whole-brain, cluster corrected to  $p < .05$  via permutation testing or Monte Carlo simulation as appropriate, will be used to identify significant associations. A three-way interaction of change in value by morph by training condition will indicate neural areas where learning is influenced by irritability in active but not sham training of reversals of ambiguous morphs. In addition, our *a priori* identification of the likely role of the amygdala, OFC, and ACC justifies follow-up region-of-interest analyses of mean activity or connectivity extracted from these areas with the same omnibus mixed-effects model.

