Exploratory Hypothesis 3.1: Change in irritability after training is associated with change in hostile interpretation bias. We will investigate this relationship with mixed-effects linear models with ARI (irritability), balance-point (interpretation bias), and time of assessment (pre- or post-training) as within-person variables.

Exploratory Hypothesis 3.2: Change in irritability after training is associated with magnitude of neural threat-learning system response. We will investigate this relationship with mixed-effects linear models with ARI (irritability), mean value-associated connectivity or activity in the amygdala, OFC, and ACC, and time of assessment (pre- or post-training) as within-person variables.

As requested by NIMH scientific review, I will conduct two additional, secondary analyses: 1) a mediation analysis of active IBT on change in irritability and 2) a multivariate analysis of the shared and unique effects of irritability, anxiety, and depression on hostile interpretation bias.

Power analysis. For Aim 1, a sample size of 100 achieves 80% power to detect an effect size of the expected association of at least  $r = .25$  between baseline hostile interpretation bias and baseline irritability using Pearson correlation at a one-tailed alpha of .05. Thus, the proposed study will have sufficient power to detect small to medium sized interaction effects. The study is overpowered for detecting expected effects of IBT on hostile interpretation bias which should be large. For Aim 2, a sample size of 100 likewise achieves more than 80% power to detect the expected large association between baseline irritability and learning. For imaging, using a medium effect size of a term in a general linear model ( $R^2 = .15$ ), the required sample for 80% power is 50 individuals ( $p = .05$ ). Our previous study that examined IBT-related changes to face-emotions was medium to large in the orbitofrontal cortex. Thus, the proposed study will have sufficient power to detect small to medium sized interaction effects. Aim 3 is exploratory; this study may estimate effect sizes for future research.

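### The 80% imaging power at n = 50 is for one unadjusted test at p = .05, not for the whole-brain test (voxel p < .001, cluster corrected) that decides Hypotheses 2.2 and 2.3

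*Combined protocol and SAP*

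**What the plan says.** Two parts of Section F (Data Analysis Plan) bear on this.

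- **Power analysis.** The imaging sample is sized for one term with R² = .15, called a medium effect, at p = .05: "the required sample for 80% power is 50 individuals". Sidedness is not stated for imaging. After citing an earlier orbitofrontal result, the paragraph concludes that small to medium interactions can be detected. The same conclusion also appears earlier in the paragraph, under Aim 1.
- **Hypotheses 2.2 and 2.3.** The decision rule is "A voxel-wise threshold of $p < .001$ , whole-brain, cluster corrected to" .05, and this rule "will be used to identify significant associations". The prior interest in the amygdala, OFC and ACC then "justifies follow-up region-of-interest analyses of mean activity or connectivity extracted from these areas with the same omnibus mixed-effects model". No alpha or multiplicity rule is given for these regional analyses.

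Section I (Specific Aim 2) gives the imaging subsample as 25 active and 25 sham. Under Randomization, allocation continues until each arm has 25 adolescents with acceptable data, so 50 is the analysable number.

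**The concern.** The sample size calculation and the decision rule refer to different tests. The calculation is for one pre-named quantity at an unadjusted .05. The decision rule is a search over the whole brain with a voxel threshold fifty times stricter (.05/.001 = 50), followed by a cluster-extent requirement. Nowhere do the documents give power at the voxel threshold or for cluster detection, and the power paragraph is not tied to the regional analyses.

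Hypotheses 2.2 and 2.3 belong to a Specific Aim and are not labelled exploratory. Section G says the results will form the basis for a go/no-go efficacy trial. A reader who carries the 80% over to the whole-brain map could take a null map as good evidence against a medium-sized neural effect, which the calculation does not support.

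**Working it through.** **Inputs.** n = 50, R² = .15, one term, alpha .05 and target power 80% (Section F, Power analysis). Voxel threshold .001 (Section F, Hypotheses 2.2 and 2.3). Two-sided testing is my assumption; one-sided results are shown as a range.

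**Formulas.**

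- Fisher z: r = √.15 = .387 and atanh(r) = .4086. The expected statistic is .4086 × √(50 − 3) = 2.801, and power = Φ(2.801 − critical z).
- Noncentral F with 1 and 48 df: f² = .15/.85 = .1765 and λ = .1765 × 50 = 8.82.
- Simulation of the correlation test with a random regressor, which is the nearer match because ARI is observed rather than fixed.

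**Step 1: reproduce the plan's figure (two-sided .05).**

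- Fisher z: Φ(2.801 − 1.960) = Φ(.841) = 80.0%. Required n = ((1.960 + .842)/.4086)² + 3 = 50.01, rounded up to 51.
- Noncentral F: 82.9%, required n = 47.
- Simulation: about 81%, required n about 49.

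The stated 50 is therefore a two-sided, single-test figure. A one-sided .05 would need only 37 to 41, and reading .15 as f² would need 55.

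**Step 2: same effect and n at the planned voxel threshold (two-sided .001).**

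- Fisher z: Φ(2.801 − 3.291) = 31.2%.
- Noncentral F: 31.4%.
- Simulation: 30.5%.
- One-sided .001: 38% to 40% across the three routes.
- With .15 read as f² (two-sided): 24%.

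**Step 3: what 80% at one voxel would take.** At n = 50, R² of about .28 by noncentral F. Fisher z gives tanh²((3.291 + .842)/√47) = .29. At R² = .15, n would be 103 (noncentral F) to 106 (Fisher z). These are single-voxel figures and not design requirements.

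**Step 4: cluster detection.** The documents give the voxel size (2.5 mm) and the smoothing kernel, but not the extent of the effect or the smoothness of the group maps. An illustrative simulation placed R² = .15 throughout a sphere and calibrated the cluster size to 5% familywise error over about 85,000 voxels. It assumed smoothness of 6 to 10 mm and shared between-person noise of 0 to 0.6. Power was roughly:

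| Sphere radius (assumed) | Cluster power |
|---|---|
| 6 mm | 6% to 46% |
| 8 mm | 32% to 76% |
| 10 mm | 51% to 97% |
| 15 mm | 68% to 100% |

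The answer is set almost entirely by quantities that the plan does not state.

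**Step 5: the regional analyses.** One region-mean test at an unadjusted .05 has the 80% to 83% of Step 1. If Bonferroni were applied over three regions (an illustrative assumption), alpha would be .05/3 = .0167. Power would then be Φ(2.801 − 2.394) = 66% by Fisher z and 69% by noncentral F.

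**Step 6: small to medium effects.** Take R² = .05 as an illustration, so λ = 50 × .05/.95 = 2.63. Noncentral F gives 36% at .05 and 4% at .001.

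**The case against.** The strongest reply is that 31% is not the power of the planned test. No inference is drawn at one named voxel; the test is for a cluster, and Step 4 shows that an extended effect could be found with high probability. This stands. A reader might infer that the whole-brain analysis would usually miss a medium effect, or that about 103 participants are needed. The documents support neither, because they do not give the extent or smoothness on which cluster power depends.

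A second reply is that the .05 already has a place in the plan. The regions are named in advance, and the effect size is backed by an orbitofrontal result, which is regional. This is a reasonable reading of what was intended, and it points to the fix. But the text presents the regional tests as follow-up, gives them no alpha, and does not attach the power figure to them.

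It could also be said that the .05 in the power sentence is the cluster-corrected level. That fails. The cluster .05 is a familywise rate over the brain, applied only to voxels that have already passed .001, whereas a one-term R² calculation uses no search volume, smoothness or extent.

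Finally, Specific Aim 2 speaks of "response while learning new associations during active IBT will be related to clinical irritability", so a reader might recompute power on the 25 actively trained participants alone. Section F does not plan that for these hypotheses. Its second-level model includes training condition and so uses all 50.

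**Conclusion.** The point holds as a mismatch between the power statement and the decision rule. It is not an arithmetic error, since the plan's own figure reproduces, and the p < .001 threshold is not itself at fault. The 80% belongs to one unadjusted test of a single pre-named quantity. For the whole-brain test that declares Hypotheses 2.2 and 2.3, power is not stated and cannot be derived from the documents. At a given voxel with the assumed effect it is about 31% (38% to 40% one-sided); for a cluster it may be lower or higher. The imaging claim about small to medium interactions is unsupported even at .05.

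These figures rest on two-sided testing and on the plan's own single-term R². The planned term is an interaction in a mixed model with morph varying within person, and no variance components are given that would allow a closer calculation. The harm is a risk of misreading: no section says that a null map will count against a neural target, and Section G also describes the project as generating hypotheses.

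**What to change.** In Section F, Power analysis, replace the imaging sentence with text such as:

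> n = 50 gives about 80% power (80% to 83% by method) for one pre-named region-mean term with R² = .15 at two-sided .05 without multiplicity adjustment (about 66% to 69% if Bonferroni-adjusted over three regions, as an illustration). Whole-brain cluster power was not calculated. At a single voxel with R² = .15, power at two-sided p < .001 is about 31%, and 80% at a voxel needs R² of about .28.

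Then:

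- delete the statement, where it follows the imaging calculation, that power suffices for small to medium interactions;
- state the alpha and any multiplicity rule for the regional analyses, so that the reader knows which of the figures above applies;
- add that a null whole-brain map does not rule out a medium effect.

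The cost is wording only. Sample, threshold and procedures do not change, but the stated imaging power becomes less favourable.

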### **G. Summarize Knowledge to be Gained:**

The NIMH requires evidence of neural or cognitive mechanism prior to continuing the development of novel treatments. This study is designed to establish the two most likely targets of IBT's effect on irritability. These neurocognitive targets are hostile interpretation bias and learning circuitry response. The successful completion of this proposed research will establish the neurocognitive basis for a go/no-go randomized controlled trial of the efficacy of IBT for clinical irritability. Next, as evidenced in the analytic plan, this project is designed to provide hypothesis-generating information about hostile interpretation bias and threat learning in irritable youth, who may be vulnerable to aberrant threat processing. This contribution would be significant because it will further develop an evidence based, nonpharmacologic, and inexpensive treatment for irritability that targets specific neurocognitive mechanisms

